Official Title: Development of Mechanistically Informed Therapy for Task-Specific Dystonia Using Noninvasive Neuromodulation

Protocol#: Pro00094131

NCT#: NCT06422104

Document Date: 11/09/2023 (Version 1.31)

General Information

*Please enter the full title of your protocol:

Development of Mechanistically informed Therapy for Task-Specific Dystonia Using Noninvasive Neuromodulation

*Please enter the Short Title you would like to use to reference the study:

Neuromodulation Therapy for Task-Specific Dystonia

* This field allows you to enter an abbreviated version of the Study Title to quickly identify this study.

Standard Research Summary

Purpose of the Study

- Objectives & hypotheses to be tested

The overarching goal of this study is to develop a non-invasive neurostimulation therapy for patients with focal hand dystonia (FHD). Specifically, the data obtained from this study will determine if engaging the striatum during non-invasive brain stimulation in the form of Transmagnetic Stimulation (TMS) can provide prolonged improvement of dystonic symptoms. Previous work in this field has advanced our understanding of regional brain circuit disruptions in dystonia and shown some efficacy in improving focal dystonia using non-invasive brain stimulation, though as of yet the effects are relatively modest and not enduring.

Goal: To characterize baseline behavioral and structural differences between focal hand dystonia subjects and healthy volunteers and evaluate safety and feasibility of neurostimulation therapy.

Visit 1: 70 FHD subjects and 70 healthy volunteers (HV) will be recruited to provide writing samples on digital writing tablet at Duke Brain Stimulation Research Center (BSRC).

Visit 2: A small cohort of 70 FHD subjects and 70 HV from visit 1 will be recruited to undergo functional MRI brain at Duke Brain Imaging and Analysis Center (BIAC). Data from visit 2 will also be used to localize the cortical target for TMS stimulation in visits 3, 4 and 5. Overall, data from visits 1 and 2 will be used to establish baseline outcome measures for visits 3, 4 and 5.

A urine drug screen and pregnancy test prior to visits 3-5.

[figure not shown]
[figure not shown]

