Furthermore, a meta-analysis of 5 TMS studies in WC dystonia subjects also demonstrated consistent albeit short-term benefit when TMS was applied at premotor cortex supporting its role in engaging dystonia brain circuitry(38–43) and supporting the idea that these regions are also linked by a common connection. A second potential cortical target is primary sensory cortex. Previous connectivity analysis in WC subjects demonstrated decreased functional connectivity between putamen and primary sensory cortex(27). Among the previous studies applying TMS to WC subjects, the study that showed the longest benefit (2weeks) targeted the primary sensory cortex(44). In this study, TMS stimulation will be applied to the premotor cortex during one visit and to primary sensory cortex during another visit to evaluate the optimal cortical target for modulating putamen activity using TMS in WC subjects.

Design & Procedures

- Describe the study, providing details regarding the study intervention (drug, device, physical procedures, manipulation of the subject or the subject’s environment, etc.). Discuss justifications for placebo control, discontinuation or delay of standard therapies, and washout periods if applicable. Identify procedures, tests and interventions performed exclusively for research purposes or more frequently than standard of care. Include alternative therapies, concurrent therapies discontinued per protocol, risk benefit ratio, and use of tissue/specimens. Discuss monitoring during washout periods if applicable. Include brief description of follow-up, if any.

Consent process and data collection will occur in a private room at the Duke Morreene Road Clinic or Duke brain Imaging Center or Duke Brain Stimulation Center in Red Zone of Duke South. All subjects

will sign an electronic single consent form uploaded to redcap or a printed hard copy. Any subject who wishes to sign their consent forms virtually, a blank consent form will be shared with subjects by redcap or emailed to them prior to the virtual visit. A phone or video visit will then be scheduled. At the virtual visit, an IRB approved study script will be used to review the research study with them for consenting purposes. The subject can then sign the consent form on redcap electronically or mail the signed hard copy to the study staff. The signed consent form will then be scanned and uploaded to Oncore and maestro care. Subjects can opt in or out of visits 2, and 3-5 of the research study.

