Visit 1: 70 HV and 70 FHD subjects will be recruited at the Duke BSRC in the Duke Main Hospital. After the study team consents the subject, the following will be obtained: Patient's medical history to evaluate appropriateness of dystonia diagnosis. Patient will also be asked about the symptoms and signs of dystonia on rating scales including Adult dystonia and disability rating scale (ADDS)(45) Burke Fahn Marsden Rating Scale (BFM) and Pain Scale.

Subjects will then be asked to perform 3 writing samples (WT-1, WT-2, and WT-3) and non-writing samples on a digital tablet. WT-1 will be a single sentence written repeatedly 10 times to quantify writing performance. WT-2 will be a different single sentence written 10 times. WT-3 will be a linguistically diverse paragraph. All writing tasks will be performed by subjects using their dominant **left or right hand**. All subjects will be videotaped from the neck down, focused on their arms and hands during the writing sampling to allow careful examination of subject's hand and finger movements for Writer's Cramp Rating Scale (WCRS)(46) by 2 expert physicians (one Duke physician and one external physician) blinded to the group identity.

The patients videos of writing assessments are reviewed by the research team to ensure no personal identifier information (face, name, DOB) is visible. Videos are then deidentified and an ID number is assigned to each video for blinding purposes. The research staff then imports the videos to a secure Duke server including DukeBox and Duke PACE environment. The external physician will only access the videos using the Duke PACE environment while the internal Duke physician may access the videos using either the Duke Neurology server, DukeBox or Duke PACE environment. The physicians will rate the participants' writing assessments using established dystonia rating scales (WCRS, BFM).

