Visit 2: 70 FHD subjects and 70 HV from visit 1 will be recruited to undergo a functional MRI brain at Duke BIAC. To assess patient's baseline, subjects will copy a sentence using their dystonic **left or right hand** in fMRI suite alternated by periods of rest using an MRI compatible digital tablet. Writing task and control motor task will be back-projected onto a screen located at the head of the MRI bed using an LCD projector. Subjects will view the screen via a mirror system located in the head coil. Task onset will be electronically synchronized with the MRI acquisition computer using Cigal computer software. Task administration and collection of writing data will be computer controlled. The scanning session will take about 1.5 hr and include structural MRI, DTI, Swan, resting state fMRI and task-based fMRI.

BOLD images will be acquired using a GE Premier Performance 3T MRI scanner, which is an improved version of GE's FDA-approved Premier system, but with better capabilities for high-resolution imaging. All operational parameters on this improved system will be within FDA guidelines to meet the same minimal risk device criteria and ensure safety of human subjects. As such, an Investigational Device Exemption (IDE) is not necessary. The research conducted under this protocol is not to evaluate the safety and efficacy of this device.

A urine drug screen and pregnancy test prior to visits 3-5.

Visits 3, 4 and 5: 5 healthy volunteers who completed visits 1 and 2 will be recruited to undergo development of TMS stimulation protocol at Duke BSRC. Following protocol development, 20 focal hand dystonia subjects who completed visits 1 and 2 will also be recruited to undergo TMS stimulation at Duke BSRC. All 25 subjects will undergo the procedure as detailed below:

[figure not shown]

Figure 3: Sequence of events for research visits 3, 4, and 5. A) Overview of TMS stimulation, writing assessment and fMRI imaging. B) TMS session will be divided into 4 blocks of writing, each 5 minutes.

1. MRI Brain images from visit 2 will be uploaded to a neuro-navigation system (Brainsight: Rogue Research, Montreal, Canada) at the Brain Stimulation Service Stimulation Service Center

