 5. Of note, although both writing task and writing assessment will comprise of a writing and non-writing sample on a digital tablet, writing assessment will additionally entail video recording of the subjects' writing from the neck down, focused on subjects' arms and hands. These recordings will be used to complete Writer's Cramp Rating Scale (WCRS)(46) and Adult dystonia and disability rating scale (ADDS)(45) by an observer blinded to treatment. Overall, writing task is different from writing assessment in that writing task will only be used as part of the investigational treatment while writing assessment will consist of outcomes measures data collected for analysis.
 6. Data from visits 3, 4 and 5 will be used to determine safety of TMS stimulation protocol and feasibility of writing task and fMRI with stimulation protocol.

Selection of Subjects

- List inclusion/exclusion criteria and how subjects will be identified.

Inclusion criteria:

Healthy Control Participants:

1. 18yrs and older
2. **Left or Right hand dominance**
3. Age-matched to Focal Hand dystonia patients
4. Must be able to sign informed consent

5. Must be literate

Focal Hand dystonia Patients:

1. 18yrs and older
2. **Left or Right hand dominance**
3. **Diagnosed with Writer's Cramp dystonia in left or right hand**
4. Must be able to sign informed consent
5. Must be literate

Exclusion criteria:

Healthy Control Participants and Focal Hand dystonia Patients (visit 1)

1. Other neurological movement disorders diagnoses including other types of dystonia, Parkinsonism, or essential tremor
2. Botulinum toxin injections within 3months of research study
3. Medications with effects on the central nervous system including anticholinergic, benzodiazepines, and muscle relaxants among others within 1 week of the study
4. No physical or occupational therapy of the upper extremities

Healthy Control Participants (visits 2-5) and Focal Hand dystonia Patients (visits 2-5):

1. Other neurological movement disorders diagnoses including other types of dystonia, Parkinsonism, or essential tremor
2. Botulinum toxin injections within 3months of research study
3. Medications with effects on the central nervous system including anticholinergic, benzodiazepines, and muscle relaxants among others within 1 week of the study
4. No physical or occupational therapy of the upper extremities
5. Any contraindications to MRI (ie: metal in body or implanted medical devices, etc)

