Participation is voluntary, and there will be no pressure or time constraints regarding the decision to participate. Healthy participants and dystonia patients may benefit from improvement in their writing task, monetary reward or compensation, and good will of helping the progress of scientific research. The information learned from this study may aid our understanding of how the brain networks in dystonia patients are different from healthy adults. This knowledge may lead us towards future therapy to improve different types of focal dystonia in adults.

MRI Adverse Events Plan:

An MRI procedure is considered to be "minimal risk" according to federal definitions. To date, no after effects have been revealed and the FDA has classified the MR procedure as possessing a "non significant risk" for the subject of study. To minimize risks, all subjects will be screened for metallic devices, implants and other contraindications to scanning. Women of child-bearing capacity will be excluded for pregnancy using a pregnancy test prior to scanning. Those unlikely to tolerate the sense of confinement during scanning will also be excluded.

Adequate safety monitoring and observation during scanning will be provided, as will measures to enhance the subject's physical and emotional comfort during the scan. It is possible that some subjects might experience minor distress by the confined and noisy conditions in the scanner. This possibility will be minimized by earplugs and headphones, and experienced technicians who will monitor all subjects for distress. In the event that a subject becomes anxious during a scan, the study will be halted. Subjects will be able to communicate with the investigators at all times using the intercom system should they wish to request that a study be terminated or have concerns or questions during the procedure. The subject is in full view of the operator at all times.

The probability of an incidental finding that might lead to the diagnosis of an unknown abnormality is greater than zero. All subjects who undergo MR-related procedures will be alerted to this possibility during the consent process. In that

event, subjects or their designated physician will be provided copies of their anatomical scans and advised to seek further evaluation if they have concerns.

TMS Adverse Events Plan:

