Writer's cramp behavioral data: Endpoints: Objective handwriting parameters of duration of writing, speed of handwriting, fluency of writing movements, axial pen pressure and interpretability of handwriting will be collected using a digital tablet and a pressure sensitive pen for data analysis. Additionally, an observer blinded to subject group will complete Writer's cramp rating scale(46) and BFM Rating Scale from video recordings of subjects performing each writing task (WT-1, WT-2 and WT-3). At the initial visit, patient's medical history will be collected to evaluate appropriateness of dystonia diagnosis. Patient will also be asked about the symptoms and signs of dystonia on rating scales including Adult dystonia and disability rating scale (ADDSD)(45) Burke Fahn Marsden Rating Scale (BFM) and Pain Scale to compare their baseline symptoms before and after all 4 visits.

Sample Size justification: A review of prior research studies employing TMS in writer's cramp and healthy volunteers measuring handwriting showed statistically significant effect sizes of 15-20% on various measures of writing performance using 6-12 subjects per group(38-40,43). A power analysis of our preliminary writing behavior data from 30 subjects in visit 1 demonstrated sample size of 60 in TMS for effect size of 30% with $\alpha = 0.05$. Assuming that I will be able to achieve similar sensitivity in writing metrics, I propose to study 20 patients in TMS group using writing task and fMRI as outcome measures for analysis (visit 1). Due to the pilot nature of fMRI and TMS stimulation parameters, the minimum number of subjects needed to calculate statistical power were selected. Therefore, in order to reach pilot data set of 20 patients in TMS group with 31% screening failure rate, we need approximately 70 FHD subjects. The 70 healthy volunteers will allow us to do a better statistical power analysis of clinical and fMRI outcomes measures to evaluate effect size for TMS As a result, we would like to increase our overall goal enrollment target to 140

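### The Visit 2 imaging cohort is set equal to the whole Visit 1 sample, so it needs 100% carry-over into an optional, more restrictive visit, and age balance among those scanned is neither protected nor checked

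*Combined protocol and SAP*

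**What the plan says.** Purpose of the Study gives the Visit 1 size: "70 FHD subjects and 70 healthy volunteers (HV) will be recruited to provide writing samples on digital writing tablet". Design & Procedures repeats it: "70 HV and 70 FHD subjects will be recruited at the Duke BSRC". For Visit 2, Purpose of the Study has "A small cohort of 70 FHD subjects and 70 HV from visit 1 will be recruited to undergo functional MRI brain", and Design & Procedures has "70 FHD subjects and 70 HV from visit 1 will be recruited to undergo a functional MRI brain at Duke BIAC". The sample size paragraph in Data Analysis & Statistical Considerations closes the count: "we would like to increase our overall goal enrollment target to 140".

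Three provisions let people leave between the two visits:

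- The consent paragraph of Design & Procedures says "Subjects can opt in or out of visits 2, and 3-5 of the research study".
- Selection of Subjects has a separate exclusion list for visits 2-5. It adds MRI contraindications and contraindications on the TMS safety screen to the Visit 1 list.
- The MRI Adverse Events Plan tests for pregnancy before scanning and adds "Those unlikely to tolerate the sense of confinement during scanning will also be excluded".

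For healthy volunteers, one inclusion criterion reads "Age-matched to Focal Hand dystonia patients". It gives no matching method, caliper or ratio. The fMRI paragraph of the analysis section says that group data go into a GLM, and it lists no covariates.

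**The concern.** A subset drawn from 140 people cannot be small and also number 140. The count leaves no reserve, while the plan itself provides several ways to drop out before the scanner. No over-recruitment, replacement rule or expected loss is given for this step.

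Two things are at stake. The first is the size of the dystonia-versus-control imaging comparison. Characterising baseline differences between the groups is a stated goal, and the sample size paragraph justifies the 70 healthy volunteers partly by the fMRI outcome measures. The second is comparability. Matching at recruitment balances the people recruited. If those who are not scanned differ in age between the groups, the scanned groups can differ in age even though the recruited groups did not. Without an age term in the model, part of an age effect could then be read as an effect of dystonia.

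**Working it through.** **Inputs.** Visit 1: 70 + 70 (Purpose; Design & Procedures). Visit 2: 70 + 70 from Visit 1 (same sections). Enrolment target: 140 (sample size paragraph). Screening failure: 31%, used there to get from 20 TMS patients to about 70 FHD subjects. Loss between Visits 1 and 2: not stated, so it is varied below as an assumption.

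**The plan's own derivation of 70.** This is the only origin given for the FHD number. Inflating 20 for 31% failure gives 20 / (1 − 0.31) = 28.99, so 29, not 70. The 70 therefore cannot be traced to the 31%, and it contains no visible allowance for loss before Visit 2.

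**Carry-over required.** 140 / 140 = 100%.

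**How likely that is.** If each person is lost independently with probability d, the chance that all 70 in one group go on is (1 − d)^70, and for both groups it is (1 − d)^140.

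- d = 1%: 0.99^70 = 49%; both groups 24%
- d = 5%: 0.95^70 = 2.8%; both groups 0.08%
- d = 10%: 0.90^70 = 0.06%; both groups about 4 in 10 million

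**Expected number scanned and precision.** Expected n = 70(1 − d). The standard error of a two-group difference, relative to 70 per group, is √(2/n) / √(2/70) = √(70/n). The detectable standardised difference is that of a two-sample t test (noncentral t, 80% power, two-sided 5%). The plan gives its α as 0.05; the 80% power and two-sided test are assumptions.

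| Assumed loss | Scanned per group | Relative SE | Detectable difference (SD) |
|---|---|---|---|
| 0% | 70 | 1.00 | 0.48 |
| 5% | 66.5, taken as 66 | √(70/66) = 1.03 | 0.49 |
| 10% | 63 | √(70/63) = 1.05 | 0.50 |
| 20% | 56 | √(70/56) = 1.12 | 0.53 |
| 31%, only if that rate applied here | 48.3, taken as 48 | √(70/48) = 1.21 | 0.58 |

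If 31% applied to FHD subjects alone (48 versus 70), the relative standard error is √(1/48 + 1/70) / √(2/70) = 1.11 and the detectable difference is 0.53.

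**Reverse calculation.** To scan 70 per group, Visit 1 would need 70 / (1 − d): 74 per group at 5% loss, 78 at 10% and 88 at 20%.

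**TMS cohort.** It needs 20 FHD subjects who have completed Visits 1 and 2. Even the 31% case leaves 48.

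**Age.** If the scanned groups differ by δ years in mean age and the imaging measure changes by β per year, a comparison without age is off by β × δ. The documents give neither quantity, so no figure can be attached.

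**The case against.** The strongest reply is that 70 plus 70 is a recruitment target or ceiling. On that reading a shortfall breaks no commitment. The Analysis and Statistics paragraph also lets cohort sizes for later visits, Visit 2 included, be adjusted after the Visit 1 data. This stands to the extent that a reader might infer that the stated size cannot be reached, and the documents do not support that: it is reached if nobody opts out or is excluded. But the adjustment clause rests on a new power calculation from writing data. It states no expected loss and does not resolve the conflict between the adjective and the number.

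A second reply is that 31% is not a Visit 1-to-2 rate. This stands in full. The plan links it to reaching 20 TMS patients and attaches it to no particular step, and Subject Recruitment and Compensation places in-person screening at Visit 1. It is also used only to derive the FHD number. Forty-eight scanned per group is a conditional illustration, not an expectation.

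A third reply is that matching need not fail. This also stands. No pairing is described, group-level balance may survive loss, and the same exclusions apply to both groups. Imbalance requires age-related loss that differs between groups, and the documents give no evidence of that. Nor do they say that the GLM is unadjusted; they are silent on covariates. What remains is that nothing in the plan checks the balance or guards against its loss.

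Finally, fMRI is described as pilot work and no power is claimed for this comparison, so the consequence is modest.

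**Conclusion.** The count needs correcting: Visit 1, Visit 2 and total enrolment are the same 140 people, Visit 2 is optional and more restrictive, and no loss is allowed for. Full carry-over is implausible under any but a very small loss rate; even 5% per person gives 2.8% for one group, assuming independent losses. The effect on precision is small at moderate loss (0.48 to 0.50 at 10%, 0.53 at 20%) and reaches 0.58 only if 31% is lost in both groups at this step.

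On age, the supported conclusion is that matching is unprotected and unchecked in the scanned subset and that the analysis text names no age term. It would go too far to conclude that matching is lost or that the comparison is confounded.

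Severity is minor. The TMS cohort is unaffected.

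**What to change.** 1. In Purpose of the Study and in Design & Procedures, restate Visit 2 as up to 70 per group from Visit 1, and delete the description of the cohort as small.
2. In the sample size paragraph, state an assumed range for loss between Visits 1 and 2 and give the precision of the imaging comparison across it, as in the table above. Do not enter 48 as the expected number.
3. In the fMRI data paragraph, specify age as a covariate in the FHD-versus-healthy-volunteer group GLM.
4. Add a comparison of scanned with unscanned participants, by group, on Visit 1 data, including age.

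The cost is some wording, one model degree of freedom and one descriptive table. Age must already be known to apply the matching criterion. The stated imaging sample becomes smaller, and no extra enrolment is needed.

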Visit 3, 4 and 5: 5 HV who completed visits 1 and 2 will be recruited to undergo development of TMS stimulation protocol at Duke BSRC. TMS Stimulation will be provided up to 20 minutes (at 10Hz) with a writing sample during stimulation. Subjects will also perform a writing assessment before and after each stimulation block. An fMRI will be performed after completion of each TMS stimulation session.

20 focal hand dystonia subjects who completed visits 1 and 2 will also be recruited to undergo 3 visits of TMS stimulation at Duke Brain Stimulation Center. The 3 visits will each be 1 week apart. 2 visits will involve active TMS and 1 visit will be sham TMS. During one of the active TMS visits, TMS coil will be applied to the premotor cortex for brain stimulation while during the other active TMS visit, TMS coil will be applied to the primary sensory cortex. TMS stimulation protocol will consist of 10Hz stimulation for up to 20 minutes with a writing task during the stimulation block. Subjects will undergo a writing assessment before and after each stimulation block and complete TMS side effects survey. Writing task is different from writing assessment in that writing task will only be used as part of the investigational therapy while writing assessment will be data collected for outcomes measures. fMRI will be performed after completion of each of the 3 TMS visits.

Background & Significance

- Should support the scientific aims of the research

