 3. Healthy volunteers will undergo TMS stimulation protocol development. Subjects will receive 10Hz active stimulation at premotor cortex during one visit and primary sensory cortex during another visit for up to 20 minutes with stimulation intensity up to 120% of resting motor threshold which is within the published safety guidelines (47) and based on previously published protocol used in multiple human studies(13–16). The resting motor threshold is a baseline stimulation intensity determined using the protocol in step 2. Additional stimulation parameters including duration of continuous stimulation, interstimulus interval, stimulation intensity, orientation of magnetic coil, biphasic or monophasic stimulation will be developed with healthy volunteers based on the published safety guidelines(47), writing assessment (includes writing and non-writing sampling) and feasibility within 20 minutes stimulation paradigm.
 4. WC subjects will undergo TMS stimulation visits 3, 4 and 5. 2 visits will include active TMS stimulation while the remaining one visit will be a control sham stimulation. Of the 2 active TMS stimulation visits, subjects will receive TMS at premotor cortex during one visit and at primary sensory cortex during the other active TMS visit. The dosage of active stimulation will be 10Hz for up to 20 minutes with resting motor threshold up to 120% which is within the published safety guidelines (47) and based on previously published protocol used in multiple human studies(13–16). During both active and sham stimulation blocks, subjects will be asked to perform a writing task of writing a diverse paragraph as an online stimulation task. The stimulation block will be preceded and followed by a writing assessment and TMS acute side effects survey to assess safety of the stimulation. Visit 3, 4, and 5 will occur 1 week apart. Subject will undergo fMRI after each of the 3 TMS visits.

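### The sham-versus-active handwriting ANOVA merges the two active sites, has no period term and leaves out the same-session pre-stimulation writing value; the readable text gives no condition order

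*Combined protocol and SAP*

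**What the plan says.** Under Purpose of the Study (Visit 3, 4 and 5) and Design & Procedures, step 4, each of 20 patients has one premotor, one primary sensory and one sham session. On spacing: "The 3 visits will each be 1 week apart". No washout reason is given, and no readable section states which condition comes first or whether order is randomised or counterbalanced.

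On measurement: "Subjects will undergo a writing assessment before and after each stimulation block". So writing has its own baseline at every TMS visit. For Visits 3 to 5 the only baseline the plan names is an earlier one: "data from visits 1 and 2 will be used to establish baseline outcome measures for visits 3, 4 and 5".

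Under Analysis and Statistics, the sham-versus-active comparison is a two-way repeated-measures ANOVA for each handwriting measure. Its factors are writing during versus after stimulation and sham versus active, and both are called between-subject. Premotor and sensory stimulation share one active level. No period, site, change score or covariate is named.

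Background & Significance explains why there are two sites: "to evaluate the optimal cortical target for modulating putamen activity using TMS in WC subjects". For fMRI, scans follow each TMS visit, and Visit 2 is the only scan before any stimulation.

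**The concern.** The design is a three-condition, three-period crossover, but the stated analysis does not treat it as one. Three things follow.

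- **Sites.** With a single active level the ANOVA gives no premotor-versus-sensory contrast. If only one site works, pooling dilutes its effect.
- **Period.** Patients write repeatedly at each of three weekly visits. If performance improves with practice, whichever condition comes later looks better unless order is balanced.
- **Baseline.** Neither level of the first factor is a pre-stimulation value. A Visit 1 or 2 baseline is one number per patient, so it cancels from any within-patient contrast and cannot adjust for the patient's state at the start of each session.

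At stake are the sham-versus-active handwriting result and what can be said about the two sites. An order confound cannot be repaired once the sessions have been run. The safety and feasibility aims are not affected.

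**Working it through.** The plan states no figure on this point to reproduce. The checks below ask what the stated model can and cannot identify.

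**Inputs from the plan.** 20 patients; 3 conditions (P premotor, S sensory, H sham); 3 visits. **Assumed.** Practice gain of g within-patient SD per visit; a fraction c of an active effect d remaining one week later; pre-post correlation r. The documents give none of these.

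**1. Can condition and period be separated?** Fit 20 patient columns, 2 condition columns and 2 period columns, 24 in all. With one order for everyone the design matrix has rank 22, so condition and period are completely confounded, and adding a period term would not help. With 3 or 4 patients in each of the six orders the rank is 24. With 60 observations, the residual degrees of freedom are 60 − 24 = 36, against 60 − 22 = 38 without period.

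**2. Practice under one fixed order, no TMS effect, post-stimulation values.** Visit means are 0, g, 2g. Pooled active minus sham:

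- sham first: (g + 2g)/2 − 0 = +1.5g
- sham second: (0 + 2g)/2 − g = 0
- sham third: (0 + g)/2 − 2g = −1.5g

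Contrast variance, in within-patient variance units: (1/4 + 1/4 + 1)/20 = 0.075. Noncentrality is 1.5g/√0.075. Two-sided 5% t test, 38 df, sham first or third:

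| g | noncentrality | false-positive rate |
|---|---|---|
| 0.1 | 0.55 | 8% |
| 0.2 | 1.10 | 19% |
| 0.3 | 1.64 | 36% |

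A two-level paired test with 19 df gives 8%, 18% and 34%. If the between-subject label is taken literally, the result differs. Simulation (20,000 runs, sham first, assumed intraclass correlation 0.5) gives about 2%, 5% and 13%, and at 0.7 about 0.3%, 1% and 4%. That test is mostly conservative, because patient differences are left in the error term.

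**3. Carryover, algebra only.** Take first-order carryover, equal at both sites, and post-stimulation values. The bias in pooled active minus sham is:

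- sham first: the second active visit gains c·d, so +c·d/2
- sham second: sham gains c·d, so −c·d
- sham third: one active visit and sham each gain c·d, so c·d/2 − c·d = −c·d/2

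The average over balanced orders is (0.5 − 1 − 0.5)/3 = −1/3 of c·d. Balancing therefore removes practice bias but not all carryover bias.

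**4. What the same-session baseline does.** After minus before removes practice and residual effects if they are additive and stable within the session. A covariate with slope b leaves a share 1 − b of the carryover bias. Variance relative to post values alone is 2(1 − r) for the change score and 1 − r² for the covariate (b = r):

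| r | change score | covariate | carryover bias left by covariate |
|---|---|---|---|
| 0.3 | 1.40 | 0.91 | 70% |
| 0.5 | 1.00 | 0.75 | 50% |
| 0.7 | 0.60 | 0.51 | 30% |

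For the pooled contrast under balanced order, mean squared errors are equal when (c·d/3)² = 0.075, that is c·d = 0.82 within-patient SD. Below that the covariate version does better.

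**5. fMRI.** If Visit 2 is the pre scan for all three conditions, then (post P − Visit 2) − (post H − Visit 2) = post P − post H. The baseline cancels, so it cannot remove carryover.

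**The case against.** **The order may exist.** Several figures are not shown, and one could carry a visit schema. The caption "Figure 3: Sequence of events for research visits 3, 4, and 5" goes on to describe stimulation, writing, imaging and the blocks of a session, but other figures have no readable caption. A reader might infer that the trial is unrandomised or runs one fixed order. The documents do not show that, and the 8% to 36% range applies only if it is so. With balanced order the practice bias is zero.

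**The target-choice aim concerns putamen activity.** That is an imaging outcome, so the aim does not by itself oblige the handwriting ANOVA to separate sites. No premotor-versus-sensory handwriting test is stated, so no error rate can be charged to one. What stands is that handwriting is an outcome of the TMS sessions and the stated model cannot show which site changed it.

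**Carryover may be negligible.** The longest benefit cited is 2 weeks, after sensory-cortex stimulation, and a reader might infer that a 1-week gap is therefore contaminated. The plan does not give that study's number of sessions or dose, and it says of earlier work that "the effects are relatively modest and not enduring". No value of c can be taken from the documents. Carryover also needs a real effect, so it cannot create a false positive when neither site works.

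**Before-and-after comparison is not absent from the plan.** The statistical section plans one for the dystonia, disability and pain scales. The gap is confined to the handwriting ANOVA.

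**This is a pilot.** True, and it limits the harm. But the sham-versus-active test is planned, and Data & Safety Monitoring requires the statistical approach to be settled and clear beforehand.

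**Conclusion.** The point holds for the stated handwriting analysis, whatever the missing figures show. The model merges two sites, omits period, mislabels within-patient factors as between-subject, and gives no role to a baseline that is collected at every TMS visit.

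The consequence for error rates is conditional. The rise from 5% to about 8% to 36% needs three assumptions: one fixed order with sham first or last, practice of 0.1 to 0.3 within-patient SD per visit, and a within-patient error term. With sham second, or with balanced order, the pooled practice bias is zero. Carryover bias has a known form but no documented size. Whether the change score or the covariate should be primary is a trade-off that depends on unknown r and c·d; the documents do not settle it.

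**What to change.** 1. **Order.** State the condition order in the text, or point to the figure or list that sets it. If none is set, randomise the 20 patients across the six orders, 3 or 4 per order, with the two extra patients in orders that start with different conditions.
2. **Handwriting model.** For each measure, replace the sham-versus-active ANOVA with a within-patient model with condition (premotor, sensory, sham) and period. Use the same-session pre-stimulation value as baseline, by covariate or change score. Choose one as primary in advance and report the other as sensitivity.
3. **Contrasts.** Prespecify premotor minus sham, sensory minus sham, and premotor minus sensory.
4. **fMRI.** Compare the conditions by site. State that Visit 2 is the only scan before any stimulation, and report possible carryover as a limitation.

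**Cost.** A randomisation list if none exists, a short amendment and analysis wording. Period takes 2 degrees of freedom (38 to 36). It raises contrast variance from 0.075 to at most 0.0758 (pooled) and from 0.100 to at most 0.1008 (two conditions), about 1%. If the change score is primary, variance exceeds that of post values alone when r is below 0.5 (1.40 times at r = 0.3). If the covariate is primary, part of any carryover bias remains.
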